10. STATISTICAL CONSIDERATIONS

10.1 Study Endpoints

10.1.1 *Primary endpoint*

Undetectable PSA with recovered testosterone (non-castrate defined as testosterone > 150ng/dL) at 24 months. Undetectable is defined as PSA < 0.05 ng/ml. For institutions where the lower limit of detectable is 0.10 ng/ml, then undetectable will be defined as PSA <0.10 ng/ml.

10.1.3 *Secondary endpoints*

- Undetectable PSA at 5 months (with the combination of durvalumab and olaparib, no ADT)
- Safety of the combination of durvalumab and olaparib will be determined by the summary of AEs

10.1.4 *Exploratory endpoints/correlative studies*

- Measurement of patient reported toxicities using PRO-CTCAE at screening, cycle 5, cycle 11, and EOT. Changes over time and comparison to clinician reported toxicities (CTCAE v5.0)
- Blood biomarkers at cycle 1, cycle 2, cycle 5, cycle 11, and end of treatment: PBMCs collected to assess immunomodulation, for example, changes in T -cell populations over time, multiplex cytokine analysis, tumor associated antigens; cfDNA will also be collected at cycle 1, cycle 5 and end of treatment for potential future use.
- Archival tissue for analysis of immune activating genes and PDL1 expression
- Undetectable PSA at 11 months (irrespective of testosterone level)
- PSA PFS
- Change in PSA doubling time relative to trial entry

10.2 Sample Size Determination

The primary objective of the study is to determine the efficacy of the combination of olaparib with durvalumab in subjects with biochemically recurrent castration sensitive disease. The primary endpoint of the study is maintaining an undetectable PSA with recovered testosterone at 24 months and this event is defined as a success. Subjects that withdraw prior to the 24 month follow up time are deemed as failures for the primary endpoint. A single stage design that differentiates between population success rates of 0.15 and 0.35 will be used to assess treatment activity.⁶³

Thirty-two subjects will be accrued to this trial. If eight or more successes are observed, it is concluded that the therapy is sufficiently active to warrant further study. This design has power greater than 0.90 for a population success proportion of 0.35 using a one-sided test with size 0.10 for the population success rate 0.15.

In addition to the evaluation of the primary endpoint, the study will be monitored for unacceptable toxicity, which is defined as Grade 3 or greater immune related toxicity requiring steroids or \geq Grade 3 non-immune toxicity requiring trial discontinuation. The stopping rule for excessive toxicity and the corresponding power calculation is provided in the table below.

Toxicity	# of toxicities needed to stop the study	Toxicity rate in the population	Probability boundary is crossed
\geq Grade 3 immune related toxicity requiring steroids or \geq Grade 3 non-immune toxicity requiring trial discontinuation	4 in the first 8 subjects	0.15	0.11
	5 in the first 16 subjects 7 in the first 24 subjects 9 within 32 subjects	0.35	0.89

10.3 Analysis Populations

10.3.1 Intent-to-treat/Response-to-treatment/Evaluable population

All subjects who meet eligibility criteria and receive at least one dose of study drugs will be included in the main analysis of efficacy, even if there are major protocol deviations (e.g., incorrect treatment schedule or drug administration).

Conclusions are to be based on the population of all eligible subjects. Subanalyses may be performed on various subsets of subjects, such as those with no major protocol deviations or those who continued in the study for the entire treatment period (i.e., did not withdraw prematurely). Subanalyses will not serve as the basis for drawing conclusions concerning treatment efficacy.

10.3.2 Safety population

All subjects enrolled in the study who receive at least one dose of study drugs will be included in the safety analysis population and considered evaluable for toxicity and safety from the time of their first dose.

10.4 Safety Analysis

10.4.1 Evaluation of adverse events

Treatment-emergent adverse events will be summarized (number and percentage of subjects) for all subjects who receive at least one dose of both investigational therapies. Adverse event summaries will be organized by body system, frequency of occurrence, intensity (i.e., severity grade), and causality or attribution. Subjects who experience an adverse event more than once will be counted only once. The occurrence with the maximum severity will be used to calculate intensity.

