Most of the ADT therapies approved for prostate cancer have been on the basis of an equivalent effect on serum testosterone levels, or an improved safety profile relative to other available agents.⁴⁹⁻⁵¹ None have shown superiority in a cancer specific outcome such as an improvement in disease related symptoms, time to progression or overall survival. A Canadian study comparing intermittent versus continuous ADT in non-metastatic biochemically recurrent prostate cancer showed no difference in cancer specific outcomes, but an improvement in prostate cancer and therapy related adverse events for men treated on the intermittent approach.⁵² With an intermittent approach, men receive ADT for a fixed period of time in which PSA declines, then ADT is intentionally held and not restarted until the PSA again begins to rise. Many have explored the approach with “on cycles” of varied duration, but in most studies, the maximal response is observed by 8 months of ADT, and 6-9 months is standard.⁵³ Castrate levels of testosterone can be achieved within 48-72 hours with the administration of a GnRH

antagonist, degarelix. ADT has been shown to induce apoptosis of prostate cancer cells;⁵⁴ potentially leading to the release of tumor antigens.

Although ADT serves as the primary basis of treatment in recurrent non-castrate (castration sensitive) biochemically recurrent prostate cancer that is at risk of metastatic recurrence, lowering testosterone to castrate levels comes with significant quality of life disturbance to men; this includes decreased libido, erectile dysfunction, fatigue, muscle loss, weight gain, hot flashes, bone density loss, and potentially increased risk of cardiovascular events, cognitive impairment, and diabetes.⁵⁵⁻⁵⁷ As a consequence, many patients at risk for developing lethal forms of the disease are appropriately interested in alternatives to ADT, in hopes of avoiding ADT toxicities and preventing or delaying CRPC.

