PARP inhibition in subjects with prostate cancer harboring HRR mutations will reduce tumor burden and cause apoptosis of the cell, leading to neoantigen release, activation of the cyclic GMP-AMP synthase (cGAS)-Stimulator of Interferon Genes (STING) pathway, which in combination with PDL1 blockade may lead to durable responses. This combination may be effective in treating recurrent prostate cancer without the use of ADT, a maneuver which is associated with only temporary response, an inability to cure, and significant quality of life detriment. For those who do not achieve an undetectable PSA with normal testosterone at 4 months, ADT for a fixed course will be added starting the following cycle to determine if they can be "salvaged" with triplet therapy, as ADT has been demonstrated to increase cytotoxic T cell proliferation and will reduce tumor burden.

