2.2 Secondary Objectives

- To determine if a non-castrating regimen can provide disease control as measured by an undetectable PSA (without ADT) at 5 months (cycle 5).
- To evaluate the safety of the combination of olaparib and durvalumab

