5. TREATMENT/INTERVENTION PLAN

This is a phase II, single arm, multi-center trial that will evaluate the combination of olaparib 300mg twice daily (600mg total daily dose) with durvalumab 1500mg IV monthly in biochemically recurrent castration sensitive prostate cancer. The trial will be conducted at sites who are members of the PCCTC Network.

As seen in the trial design (Figure 2), subjects will be treated concurrently with olaparib + durvalumab continuously for 24 months. After the first 4 months, if a subject fails to achieve an undetectable PSA with the combination of olaparib and durvalumab, ADT will be added for 6 months (starting at Cycle 5) while continuing treatment with olaparib and durvalumab. For subjects who have an undetectable PSA [PSA of <0.05 or PSA <0.10] for institutions where this is the lower limit of detection] after the first 4 months of treatment, they will continue on the combination of olaparib + durvalumab continuously for 24 months (without ADT). As long as it is believed that subjects are clinically benefiting, they will remain on treatment for up to 24 months with olaparib and durvalumab. For example, a subject with a PSA reduction that does not achieve an undetectable PSA would be allowed to remain on study for the duration of the trial. Subjects who meet progression criteria while on active therapy would come off of trial. If subjects respond and later progress in the one-year follow-up period (beyond 24 months), they will be allowed to be re-induced with the combination.

Figure 2. Study schema for olaparib and durvalumab in subjects with castration-sensitive prostate cancer (biochemical recurrence) harboring DNA damage repair mutations

DDR deleterious mutations (somatic or germline) will include BRCA1 (breast cancer susceptibility gene), BRCA2, ATM (ataxia telangiectasia mutated serine/threonine kinase), CHEK2, FANCA, RAD51C, RAD51D, PALB2, BRIP1, BARD1, and CDK12. Mutations may be truncating, splice site mutations, missense or homozygous deletions. Subjects will be allowed on trial using local testing, previously obtained genomic testing from a validated lab (e.g., expedited germline testing from Color), or via archival or fresh tissue.

The following assessments and procedures will occur during the study. A schedule of assessments is provided in Appendix B.

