10.5 Statistical Procedures and Analysis

Summary statistics include the number of observations, mean, standard deviation, median, minimum, and maximum values.

Statistical methods for the analyses

An exact binomial test will be used to evaluate the efficacy of the 24 months undetectable PSA endpoint. In addition, the proportion of subjects that attain an undetectable PSA at (1) 5 months, (2) 11 months, and (3) 24 months will be computed along with their attendant 95% confidence intervals. The probability of PSA progression over time will be estimated using the cumulative incidence function.

A paired t-test will be used to compare the PSA doubling time at 24 months to the PSA doubling time at study entry.

Kendall's tau with longitudinal data will be used to compare patient recorded toxicities to physician recorded toxicities over time.

The immunologic profile of patients over time will be described using nonparametric kernel smoothing.

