APPENDIX B: STUDY CALENDAR

(A cycle = 28 days; a month = 28 days)

	Screening		Treatment/Intervention Period									End of Treatment (EOT) within 30 days of last dose	Follow Up ^s	
			Cycle 1		Cycle 2		Cycle 3	Cycle 4	Cycle 5	Cycle 6	Cycle 7- Cycle 24			
	Day -42 to Day -1	Day -14 to Day -1	Day 1 (± 3 d)	Day 15, (± 3 d)	Day 1 (± 3 d)	Day 15 (± 3 d)	Day 1 (± 3 d)	(± 7 d)						
Informed consent and research authorization/ HIPAA form ^a	X													
Demographics, medical history, histologic confirmation	X													
Physical examination, Vitals (Blood Pressure, Pulse, Temperature), weight ^b	X		X	X	X	X	X	X	X	X	X	X	X	
Height	X													
12-lead EKG	X													

Olaparib + Durvalumab
Memorial Sloan Kettering Cancer Center

c17-192

	Screening		Treatment/Intervention Period								End of Treatment (EOT) within 30 days of last dose	Follow Up ^s
			Cycle 1		Cycle 2		Cycle 3	Cycle 4	Cycle 5	Cycle 6		
	Day -42 to Day -1	Day -14 to Day -1	Day 1 (± 3 d)	Day 15, (± 3 d)	Day 1 (± 3 d)	Day 15 (± 3 d)	Day 1 (± 3 d)	(± 7 d)				
Performance status	X		X	X	X	X	X	X	X	X	X	X
Concomitant medications	X		X	X	X	X	X	X	X	X	X	X
Adverse Events	X		X	X	X	X	X	X	X	X	X	X
Radiologic evaluations and measurements ^c	X		For non-metastatic, rising PSA subjects, radiologic tests are performed at Cycle 5 (+/- 2 week), Cycle 24 (+/- 2 week) or at EOT (+/- 2 week) if discontinued sooner.								X ^d	
CBC w/ diff plts ^e		X	X	X	X	X	X	X	X	X	X	X
Comprehensive Metabolic Panel ^f		X	X	X	X	X	X	X	X	X	X	X
Coagulation Tests ^g		X										
PSA ^h		X	X		X		X	X	X	X	X	X
TFTs ⁱ		X			X			X		X	X	X
Testosterone ^j		X								X	X	
Hepatitis Panel		X										
HIV		X										
Urinalysis ^k		X										

Olaparib + Durvalumab
Memorial Sloan Kettering Cancer Center

c17-192

	Screening		Treatment/Intervention Period								End of Treatment (EOT) within 30 days of last dose	Follow Up ^s
			Cycle 1		Cycle 2		Cycle 3	Cycle 4	Cycle 5	Cycle 6		
	Day -42 to Day -1	Day -14 to Day -1	Day 1 (± 3 d)	Day 15, (± 3 d)	Day 1 (± 3 d)	Day 15 (± 3 d)	Day 1 (± 3 d)	(± 7 d)				
PBMC ^t		X		X					X		X	X
PRO-CTCAE ^m	X								X		X	X
cfDNA ⁿ		X							X			X
PDL-1 Expression (archived tissue) ^o	X											
Tissue Sequencing ^p	X											
Normal Sample ^q	X											
Olaparib Administration ^r								X				
Durvalumab Administration ^r								X				
ADT Administration ^r								X				

- a. Informed consent and radiologic assessments should be obtained within 42 days.

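### The all-cause adverse event summary does not separate olaparib–durvalumab time from the six-month ADT course and testosterone recovery, so rates for shared terms such as fatigue cannot be read as doublet rates

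*Combined protocol and SAP*

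**What the plan says.** Section 2.2 sets the objective: "To evaluate the safety of the combination of olaparib and durvalumab". Section 10.1.3 says how it will be met: "Safety of the combination of durvalumab and olaparib will be determined by the summary of AEs". ADT appears in neither statement.

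Section 5 gives ADT to men without an undetectable PSA after four months: "ADT will be added for 6 months (starting at Cycle 5) while continuing treatment with olaparib and durvalumab". Appendix B fixes the time unit: "A cycle = 28 days; a month = 28 days".

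Section 10.4.1 describes the analysis: "Treatment-emergent adverse events will be summarized (number and percentage of subjects) for all subjects who receive at least one dose of both investigational therapies". Summaries are arranged by body system, frequency, severity and causality. A man with repeated occurrences counts once, at the highest grade. No stratum for ADT, no treatment period and no cut-off at ADT start is specified there or elsewhere in Sections 10.4 and 10.5.

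Section 7.2.3 requires a five-level causality grade for every event, judged against the investigational agent or agents. The SAE reporting section (7.3.1) asks for causality against all study medications, but only for SAE reports.

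**The concern.** Section 1.2.10 lists the effects of castration: "this includes decreased libido, erectile dysfunction, fatigue, muscle loss, weight gain, hot flashes, bone density loss", among others. Fatigue also appears among the common events for olaparib (Section 1.2.5) and durvalumab (Section 1.2.7). A man can thus report the same term because of either study drug, ADT or slow testosterone recovery, and the planned table shows one entry for him.

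Section 1.3 presents the doublet as a way to avoid the quality-of-life cost of ADT. A reader of the results will want to know how tolerable the two drugs are without castration. An all-cause table that mixes doublet, triplet and post-ADT time does not answer that for shared terms. Because the table counts once at worst grade, it cannot be unpicked afterwards.

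**Working it through.** **The plan's own safety figures.** The only numerical safety statement is the toxicity stopping rule in Section 10.2 (4 in 8, 5 in 16, 7 in 24, 9 in 32). An exact sequential binomial calculation gives crossing probabilities of 0.1123 at a true rate of 0.15 and 0.8922 at 0.35, matching the stated 0.11 and 0.89. This point does not challenge that rule.

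**Exposure of one man who adds ADT and completes 24 cycles** (Section 5, Appendix B):
- before ADT: Cycles 1–4 = 4 cycles
- on ADT: Cycles 5–10 = 6 cycles; 6/24 = 25%
- after the course: Cycles 11–24 = 14 cycles
- during or after ADT: (6 + 14)/24 = 20/24 = 83%

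He is on both study drugs throughout, so all 24 cycles feed the single summary. For example, Grade 1 fatigue in Cycle 2 and Grade 2 fatigue in Cycle 8 would appear as one Grade 2 entry with no mark of ADT.

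**Exposure of the whole trial.** Assume all 32 men complete 24 cycles, a total of 32 × 24 = 768 person-cycles. The share f adding ADT is not given and is assumed. ADT-free time is 32×4 + 32×(1−f)×20, ADT time is 32×f×6, and time after the course is 32×f×14.

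| f (assumed) | ADT-free | On ADT | After ADT |
|---|---|---|---|
| 0.50 | 128 + 320 = 448 (58%) | 96 | 224 |
| 0.75 | 128 + 160 = 288 (38%) | 144 | 336 |
| 1.00 | 128 + 0 = 128 (17%) | 192 | 448 |

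Whatever f is, only the first 128 person-cycles come from all men. Later ADT-free time comes only from men with an undetectable PSA at four months.

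**What attribution can and cannot do.** Section 7.2.3 lets an investigator mark hot flashes as unrelated to the study drugs. It gives ADT no attribution of its own. ADT is listed in Section 6 (Therapeutic Agents), while Section 10.4.1 speaks of two investigational therapies, so sites may differ on whether an ADT effect counts as related. For fatigue in a single-arm trial there is no reliable basis for the choice.

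**Illustration on wholly assumed inputs.** Let q be the doublet risk of a term, f the share given ADT, and a the added ADT risk in men not already affected. The pooled all-cause rate is q + f × a × (1 − q).
- q = 0.40, f = 0.75, a = 0.30: 0.40 + 0.75×0.30×0.60 = 0.535
- q = 0.40, f from 0.50 to 0.90, a from 0.10 to 0.30: 0.43 to 0.56
- q = 0.20, f from 0.65 to 1.00, a from 0.10 to 0.50: 0.25 to 0.60

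None of these inputs is in the documents. The figures show how the mixing works and do not estimate an error in the plan.

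**The case against.** The strongest reply is that Section 10.4.1 already organizes events by attribution. Since causality is judged against the investigational agents, libido loss or hot flashes can be marked unrelated and so drop out of the related counts. That stands. A reader might infer that ADT toxicity will be reported as toxicity of the doublet, and the documents do not support that. The absence of a split is silence in Section 10, and a partial safeguard exists. It fails only for overlapping terms.

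Second, the stakes are limited. Avoidance of ADT is tested by the other secondary endpoint, undetectable PSA at five months without ADT. PRO-CTCAE is collected at screening, Cycle 5, Cycle 11 and end of treatment, which brackets the scheduled ADT course. The stopping rule counts only Grade 3 or higher events that need steroids or trial discontinuation, which typical ADT effects would seldom be. This also stands, and it places the point among reporting improvements.

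Third, a reader might take ADT-free time alone as the answer on doublet safety. That is unsound. A man who adds ADT contributes only 4 of 24 cycles to it, its later part is selected on PSA response, and late events in ADT-treated men, such as MDS/AML (an event of special interest in Section 7.1.10), would vanish from the result.

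Fourth, one might extend the point to the immune analysis. Section 1.3.2 states that "ADT has been demonstrated to increase cytotoxic T cell proliferation and will reduce tumor burden", and Section 10.5 that "The immunologic profile of patients over time will be described using nonparametric kernel smoothing". A single pooled curve is not stated there. The objective is exploratory, concerns the regimen, and relies on samples kept for later analysis. No planned conclusion would credit the doublet with an ADT effect.

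**Conclusion.** The point holds in a limited form. The safety objective names the doublet, but the all-cause summary does not distinguish doublet-only time from the ADT course and testosterone recovery, and causality against ADT is not specified. Rates of shared terms, fatigue above all, cannot be read as doublet rates. For a man who adds ADT and completes treatment, 83% of his cycles fall during or after ADT. The effect on any event rate cannot be computed from the documents.

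No endpoint, sample size or error rate is affected. The full table remains a valid description of what happened over 24 months under the protocol strategy. The conclusion assumes that the single summary is applied as written, with no split added in table shells that are not shown.

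**What to change.** Keep the full 24-month summary as the overall safety result. Add to Section 10.4.1 a tabulation by onset period:

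- (a) before any ADT, with Cycles 1–4 in all men shown separately from later cycles in men never given ADT;
- (b) from the first ADT dose until the first testosterone above 150 ng/dL recorded after the course, with men who never recover staying in (b);
- (c) after recovery.

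Give the number at risk and person-cycles for each period. Count each man once per term within a period, and state how an event that starts in one period and worsens in the next is handled. Interpret doublet safety from (a) and (c) together with the overall table, never from (a) alone. State that comparisons by ADT receipt are descriptive, because ADT is given in response to PSA. State also that the (b)/(c) boundary is approximate: Appendix B schedules testosterone at Cycles 6 and 11 and then every other month from Cycle 12, so recovery may be recorded about two months late.

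Optionally, show the exploratory immune profiles after Cycle 5 by ADT received.

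The cost is wording in Section 10 and extra table columns. This assumes that the case report forms hold AE onset and ADT dates, which is likely but not shown. The downsides are small cells and an imprecise recovery date. No treatment, visit or sample size changes.

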In the event of a \leq Grade 2 infusion-related reaction, the infusion rate of study drug may be decreased by 50% or interrupted until resolution of the event (up to 4 hours) and re-initiated at 50% of the initial rate until completion of the infusion. For subjects with a \leq Grade 2 infusion-related reaction, subsequent infusions may be administered at 50% of the initial rate. Acetaminophen and/or an antihistamine (e.g., diphenhydramine) or equivalent medications per institutional standard may be administered at the discretion of the investigator. If the infusion-related reaction is Grade 3 or higher in severity, study drug will be discontinued. The standard infusion time is one hour; however if there are interruptions during infusion, the total allowed time from infusion start to completion of infusion should not exceed 8 hours at room temperature, with maximum total time at room temperature not exceeding 8 hours (otherwise requires new infusion preparation). For management of subjects who experience an infusion reaction, please refer to the toxicity and management guidelines in Appendix G.

As with any antibody, allergic reactions to dose administration are possible. Appropriate drugs and medical equipment to treat acute anaphylactic reactions must be immediately available, and study personnel must be trained to recognize and treat anaphylaxis. The study site must have immediate access to emergency resuscitation teams and equipment in addition to the ability to admit subjects to an intensive care unit if necessary.

Supply and packaging

Durvalumab (MEDI4736) will be supplied in glass vials containing 500 mg of liquid solution at a concentration of 50 mg/mL for intravenous (IV) administration.

Durvalumab (MEDI4736) will be supplied by AstraZeneca as a 500-mg vial solution for infusion after dilution. The solution contains 50 mg/mL durvalumab (MEDI4736), 26 mM histidine/histidine-hydrochloride, 275 mM trehalose dihydrate, and 0.02% (weight/volume) polysorbate 80; it has a pH of 6.0. The nominal fill volume is 10 mL.

Storage requirements

All study drugs should be kept in a secure place under appropriate storage conditions. Drug product should be kept in original secondary packaging until use to prevent prolonged exposure

to light. The investigational product label on the bottle and the Investigator Brochure specifies the appropriate storage.

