6.2 Olaparib (AZD2281, KU-0059436) (NSC#: 747856)

Description

Olaparib is a potent PARP inhibitor (PARP-1, -2 and -3) that is being developed as an oral therapy, both as a monotherapy (including maintenance) and for combination with chemotherapy and other anti-cancer agents.

Molecular Formula

C24H23FN4O3

Molecular Weight

434 Daltons

Supply and Packaging

The Astra-Zeneca Pharmaceutical Development R&D Supply Chain will supply olaparib to the site. Olaparib tablets will be packed in high-density polyethylene (HDPE) bottles with child-resistant closures. Each dosing container will contain 32 tablets and desiccant. Multiple bottles of study treatment may be required for dispensing in order to make up the desired dose. Bottles will be labeled per local regulations.

Drug product Administration

Two 150mg tablets orally twice daily with or without food (600 mg total daily dose). The tablets are to be swallowed whole with water. Tablets cannot be broken, opened, or chewed.

Olaparib will be dispensed to subjects on Day 1 and every 28 days thereafter until the subject completes the study, withdraws from the study or closure of the study.

The olaparib tablets should be swallowed whole and not chewed, crushed, dissolved or divided.

If vomiting occurs shortly after the olaparib tablets are swallowed, the dose should only be replaced if all of the intact tablets can be seen and counted. Should any subject enrolled on the study miss a scheduled dose for whatever reason (e.g., as a result of forgetting to take the tablets or vomiting), the subject will be allowed to take the scheduled dose up to a maximum of 2 hours after that scheduled dose time. If greater than 2 hours after the scheduled dose time, the missed dose is not to be taken and the subject should take their allotted dose at the next scheduled time.

There are no special dosing instructions for olaparib on days when durvalumab is administered.

Labeling

Labels will be prepared in accordance with Good Manufacturing Practice (GMP) and local regulatory guidelines. The labels will fulfill GMP Annex 13 requirements for labeling. Label text will be translated into local language.

Each bottle of olaparib will have an investigational product label permanently affixed to the outside stating that the material is for clinical trial/investigational use only and should be kept out of reach of children. The label will include the dosing instructions.

The label will include the following information:

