7. SAFETY EVALUATION

7.1 Definitions

7.1.1 Adverse Event (AE)

Any untoward medical occurrence in a subject or clinical investigation subject administered a pharmaceutical product and which does not necessarily have to have a causal relationship with this treatment (ICH E2A).

An AE can therefore be any unfavorable and unintended sign (including an abnormal laboratory finding), symptom, or disease temporally associated with the use of a medicinal product, whether or not related to the medicinal product.

An adverse event will be recorded and followed from informed consent to 30 days post treatment or resolution.

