10.4.2 Evaluation of serious adverse events and premature withdrawals

Adverse events deemed serious and those resulting in treatment withdrawal or death will be summarized separately.

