10.4.4 Extent of exposure

Treatment exposure will be summarized for all subjects, including dose administration, number of cycles, dose modifications or delays, and duration of therapy.

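### The adverse event summary is limited to men dosed with both agents and bypasses the safety population; the AE collection window and the SAE rule for progression deaths also conflict

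*Combined protocol and SAP*

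**What the plan says.** **Population.** Section 10.3.2 defines the safety set: "All subjects enrolled in the study who receive at least one dose of study drugs will be included in the safety analysis population", with evaluability starting at first dose. It does not say whether one drug is enough or both are needed. Section 10.4.1 does not refer to this set and summarizes treatment-emergent AEs "for all subjects who receive at least one dose of both investigational therapies". Section 10.4.2 names no population: "Adverse events deemed serious and those resulting in treatment withdrawal or death will be summarized separately". Section 10.4.4 uses everyone: "Treatment exposure will be summarized for all subjects". Under the secondary endpoints in section 10.1, "Safety of the combination of durvalumab and olaparib will be determined by the summary of AEs".

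**Window.** Section 7.1.1: "An adverse event will be recorded and followed from informed consent to 30 days post treatment or resolution". The section 7.3.1 on reporting to the FDA and AstraZeneca (two sections carry that number) gives 30 days for non-serious AEs unless they are related to study drug, and 90 days for related events. It then requires every new AE in the 90 days after the last dose to be recorded for men withdrawn from treatment, without a causality condition. Section 10.4.1 gives no end to the treatment-emergent period.

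**Progression deaths.** Section 7.1.5 treats progression as an SAE if it leads to death or hospital admission during the study or in the 30 days after the final dose. The section 7.3.3 on deaths (again, two sections share the number) covers the study and 90 days after the last dose. It says that a death clearly caused by progression is documented but not reported as an SAE.

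**The concern.** The AE summary is the whole of the safety result in this single-arm trial. It needs one denominator and one window, and the plan fixes neither.

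Restricting the summary to men who had both agents can remove a man because of early toxicity. Section 6.1 provides a route: "If the infusion-related reaction is Grade 3 or higher in severity, study drug will be discontinued". Section 6.2 says "Olaparib will be dispensed to subjects on Day 1 and every 28 days thereafter", so a man could have a severe first-infusion reaction before he takes a tablet. If he never starts olaparib, he has been treated but is outside the 10.4.1 summary. Losses of this kind depend on outcome and would tend to understate toxicity.

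The other two conflicts act earlier, at the sites. If one site stops collecting at day 30 and another at day 90, the missing events cannot be recovered at analysis. Sites also cannot follow both instructions on a progression death, so the SAE count would depend on which section was read.

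**Working it through.** **1. The plan's own figures.** The plan gives no number on this point. The nearest are the design figures in section 10.2, and they reproduce:

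- Efficacy rule, 8 or more successes of 32, exact binomial: size at 0.15 = 0.0958 (stated 0.10); power at 0.35 = 0.918 (stated above 0.90).
- Toxicity boundary of 4/8, 5/16, 7/24, 9/32, exact recursion. The cumulative crossing probability at rate 0.15 is 0.0214, 0.0841, 0.1031, 0.1123 (stated 0.11). At rate 0.35 it is 0.2936, 0.7168, 0.8323, 0.8922 (stated 0.89).

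None of these depends on the population used in 10.4.1.

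**2. Does 10.4.1 match 10.3.2?** There are two readings of the safety population.

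- *Any study drug:* 10.4.1 contradicts 10.3.2, because one-agent men are in the safety population but not in the AE summary.
- *Both drugs:* the sections agree, but a treated one-agent man belongs to no safety population.

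He is missing from the AE summary on either reading.

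**3. Size of the population effect.** Assume all 32 men are treated. Let x be the number with a given AE, k the number who received one agent only, and a the number of those k who had the AE.

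Change = (x − a)/(32 − k) − x/32 = (kx − 32a) / [32(32 − k)]

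- Lowest value, with x = a = k (only the excluded men had the AE): −k/32.
- Highest value, with a = 0 and x = 32 − k (everyone except the excluded men had it): +k/32.
- So k = 1 gives at most 1/32 = 3.1 points, and k = 2 at most 2/32 = 6.25 points.

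| Case | All treated | Both agents only |
|---|---|---|
| x = 1, k = 1, a = 1 | 1/32 = 3.1% | 0/31 = 0% |
| x = 10, k = 1, a = 1 | 10/32 = 31.3% | 9/31 = 29.0% (−2.2) |
| x = 10, k = 1, a = 0 | 10/32 = 31.3% | 10/31 = 32.3% (+1.0) |
| x = 8, k = 2, a = 2 | 8/32 = 25.0% | 6/30 = 20.0% |

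The documents give no value for k. These are illustrations, and k = 0 gives no change.

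**4. Window.** The gap is 90 − 30 = 60 days.

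| New event on days 31–90 | 7.1.1 | 7.3.1, causality-based rule | 7.3.1, rule after withdrawal from treatment |
|---|---|---|---|
| Related | not recorded | collected | recorded |
| Unrelated, non-serious | not recorded | not collected | recorded |

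Section 7.3.1 therefore conflicts with itself on unrelated non-serious AEs. It conflicts with 7.1.1 more widely, including on related events and SAEs. No AE rate is given for those days, so no count can be derived.

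**5. Progression deaths.** During the study and up to 30 days after the last dose, 7.1.5 says SAE and 7.3.3 says not an SAE. On days 31 to 90 only 7.3.3 applies. Each death in the overlap changes the SAE count by one.

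**The case against.** The strongest reply concerns the population.

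- 10.3.2 may mean both drugs, in which case 10.4.1 departs from nothing. The objective is also the safety of the combination, so requiring both agents is not perverse.
- The excluded man is rare. Both agents start on Day 1, section 6.2 sets no order between them, and he may already have taken a tablet. Sections 5.4 and 6.5 can allow continuation on the other agent, so he might start olaparib later and enter the summary. Men who drop one agent later have had both and stay in.
- Serious, treatment-ending and fatal events are summarized under 10.4.2 without the restriction, so what is lost is mostly the remaining non-serious events.
- The k/32 bound is reached only at the extremes.

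On the window, 7.3.1 is the detailed rule and 7.1.1 one sentence in a definition. Within 7.3.1 only unrelated non-serious AEs are in dispute, and these say least about the drugs. Progression deaths are documented whichever rule is followed.

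All of this bears on size, and it stands: the effect is likely to be small. It does not remove the fault. On either reading of 10.3.2 a treated man can be left out of the AE summary. Nothing in the plan ranks 7.3.1 above 7.1.1 or resolves its internal conflict. The two instructions on progression deaths remain opposed where they overlap.

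**Conclusion.** The concern holds in all three parts. The population rule can drop treated men from the summary that defines a secondary endpoint, by at most k/32 on any AE percentage, assuming 32 treated men of whom k received one agent. Few are expected, and the effect is zero if there are none. The window conflict covers 60 days with an unknown number of events. The progression-death conflict changes the SAE count by one per death in the overlap. Few such deaths are expected, since section 3.1 requires no metastases on conventional imaging and a life expectancy of at least 52 weeks.

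The direction and size of any overall bias are not known. The consequence is confined to the AE and SAE summaries: two analysts could produce different tables, and two sites could handle the same event differently. The wording should be corrected, but the efficacy conclusion does not depend on it.

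**What to change.** - **Population.** Word 10.3.2 so that a man given either olaparib or durvalumab is in the safety population, and make 10.4.1 and 10.4.2 refer to it. Use the same denominator for exposure in 10.4.4. State which men count toward the toxicity boundary in 10.2, which also names no population.
- **Window.** Reconcile 7.1.1 and 7.3.1 to one AE collection rule, and use it to state when the treatment-emergent period in 10.4.1 ends.
- **Progression deaths.** Reconcile 7.1.5 and 7.3.3. The choice of rule is the sponsor's.

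The cost is wording only, with no extra patients and no change to the efficacy or stopping design. Slightly more AEs may be reported, and the table may include a man who did not receive the full combination, which a footnote can identify.
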